2.1.4.3 Deaths

The deaths observation periods are per the observation periods defined below.

- Death on-study: deaths occurring during the on-study observation period
- Death on-treatment: deaths occurring during the TEAE period
- Death post-study: deaths occurring after the end of the study

2.1.4.4 Laboratory safety variables

Clinical laboratory data consists of blood analysis, including hematology, clinical chemistry, and urinalysis. Clinical laboratory values will be summarized in both standard international units and conventional units when applicable.

Blood samples for clinical laboratories will be taken at designated visits (see study flowchart in [Appendix D](#)). The following laboratory data will be measured at a central laboratory:

- Hematology

- **Red blood cells and platelets:** hemoglobin, hematocrit, red blood cell, platelets count
- **White blood cells:** white blood cell, neutrophils, lymphocytes, monocytes, basophils, eosinophils
- Clinical chemistry
 - **Metabolism:** glucose (serum), creatine phosphokinase (CPK)
 - **Electrolytes and minerals:** sodium, potassium, chloride, bicarbonate (ie, carbon dioxide), calcium, phosphorus, magnesium
 - **Renal function:** blood urea nitrogen (BUN), creatinine, uric acid
 - **Liver function:** total protein, albumin, ALT, aspartate aminotransferase (AST), alkaline phosphatase (ALP), total bilirubin, Lactic acid dehydrogenase (LDH)
- Lipid parameters (fasting): total cholesterol (TC), high density lipoprotein cholesterol (HDL-C), low density lipoprotein cholesterol (LDL-C) (calculated by Friedwald equation, See [Section 2.5.1](#)), Non-HDL-C (calculated as the difference between TC and HDL-C), triglycerides (TG).
- Pancreatic enzymes: lipase, amylase.
- Beta-hydroxybutyrate (BHB)
- Markers of bone and calcium metabolism
 - 25-hydroxyvitamin D,
 - 1,25-dihydroxyvitamin D,
 - Parathyroid hormone (PTH),

Urine samples will be collected at designated visits (see study flowchart in [Appendix D](#)). The following laboratory data will be measured at a central laboratory:

- Urine dipstick includes: specific gravity, pH, protein, blood, ketones, bilirubin, urobilinogen, nitrite, and leukocyte esterase
- Urine microscopy includes, but is not limited to: detection of formed cellular elements, casts, bacteria, yeast, parasites, and crystals in centrifuged urine sediment

Serum glucose and Calculated UACR will be presented as efficacy parameters in [Section 2.4.4](#). For calculated eGFR, PCSA summaries will be presented in the safety section while descriptive summaries in the efficacy section.

Technical formulas are described in [Section 2.5.1](#).

2.1.4.5 Vital signs variables

Vital signs include: heart rate (HR), systolic and diastolic blood pressure, temperature, and respiratory rate (see study flowchart in [Appendix D](#) for designated visits). They will be performed after the patient has been seated for at least 5 minutes. Blood pressure and HR will be assessed 3 times with at least 1 minute between each measurement following the 5-minute rest period. The mean of the 3 measurements will be analyzed for each vital sign variable (HR, SBP, and DBP).

2.1.4.6 Physical examination

A complete physical exam will be performed at Visit 1 (Screening) and Visit 13(Week 26). “Normal”, “Abnormal” or “Not done” as determined by the Investigator will be reported in the e-CRF by body system.

2.1.4.7 Electrocardiogram variables

12-lead ECGs will be performed at Visit 1 (Screening), Visit 6 (Randomization) and Visit 13 (Week 26). ECG status of “normal” or “abnormal” will be reported in the e-CRF as determined by the investigator.

2.1.5 Pharmacokinetic variables

Pharmacokinetic variables include the plasma concentration of sotagliflozin and its 3-O-glucuronide metabolite in the sotagliflozin group.

2.1.6 Patient-reported outcome variables

The schedule of PQAT and TRIM-D are specified in the study flowchart in [Appendix D](#). The questionnaires can be found in the study protocol.

2.1.6.1 Patient’s qualitative assessment of treatment (PQAT)

The PQAT aims to understand patient perspective on benefit/risk of the IMP during the Treatment Period. This instrument includes a 7-point Likert Scale for the patient to evaluate his/her subjective response to the treatment (-3 to +3 including 0 for a neutral response) and 3 free-text response questions to describe key advantages and disadvantages of treatment experienced and willingness to pursue it or not.

All patients’ answers will be analyzed qualitatively and quantitatively, as relevant, using appropriate qualitative data analysis software. The analysis method for this exploratory analysis will be provided in a separate SAP and the analyses results will be documented in a separate report.

If a patient discontinues treatment with IMP during the Treatment Period, the patient will be asked to complete this qualitative assessment of treatment at time of discontinuation.

2.1.6.2 Treatment related impact measure for diabetes (TRIM-D)

The general treatment-related impact on patients’ health related quality of life (HRQoL) will be assessed using the TRIM-D questionnaire. The TRIM-D questionnaire is a 28-item measure comprising of 5 domains: Treatment Burden, Daily Life, Diabetes Management, Compliance, and Psychological Health (1). Table 4 below presents further technical details on this questionnaire.

Items are answered on a 5-point Likert scale ranging from (1) Not at all satisfied/convenient, or Never/Almost never, or Never/Almost never interferes to (5) Extremely satisfied/convenient, or Almost always/Always, or Almost always/Always interferes. Scales are converted into a score valued from 0 to 100 so that a higher score indicates a better health state (less negative impact). Score for each domain (called “domain score”) and total score are computed. See Section 2.4.7 for more details on the scoring method.

The TRIM-D variables include TRIM-D scores (total and domain scores) and the change in TRIM-D scores from baseline to endpoint.

Table 4 - TRIM-D domains and clusters

Domains	Number of Items	Cluster of Items	Item Reversion	Direction of Domains
Treatment Burden	6	1a, 2a, 2b, 2c, 2d, 2e	No	Higher score = better health state (less negative impact)
Daily Life	5	3a, 3b, 5a, 5b, 5c	Yes, for all items	
Diabetes Management	5	4a, 4b, 4c, 4d, 4e	No	
Compliance	4	6a, 6b, 6c, 6e	Yes, for all items	
Psychological Health	8	6d, 7a, 7b, 7c, 7d, 7e, 7f, 7g	Yes, for all items	

2.2 DISPOSITION OF PATIENTS

This section describes patient disposition for both patient study status and the patient analysis populations.

Screened patients are defined as all patients who signed the informed consent.

Randomized patients consist of all patients with a signed informed consent form who have had a treatment kit number allocated and recorded in the IRT database, regardless of whether the treatment kit was used or not.

For patient study status, the total number of patients in each of the following categories will be presented in the clinical study report using a flowchart diagram or summary tables:

- Screened patients
- Run-in patients: patients who had a run-in record in IRT,
- Screen failure patients (including failures during run-in) and reasons for screen failure
- Nonrandomized but treated patients
- Randomized patients
- Randomized but not treated patients
- Randomized and treated patients
- Patients who have completed the 18-week randomized core treatment period (see [Section 2.5.4](#)) as per protocol
- Patients who discontinued the IMP during the 18-week randomized core treatment period (see [Section 2.5.4](#)) and the reasons for treatment discontinuation
- Patients who have completed the entire 52-week double-blind Treatment Period
- Patients who discontinued the IMP during the entire 52-week double-blind Treatment Period and the reasons for treatment discontinuation
- Patients who have completed the study as scheduled
- Patients who discontinued the study, and the reasons for study discontinuation
- Patients' end of study status (completed, not completed) and corresponding end of treatment status (completed, not completed)
- Status at last study contact

For screened, run in, screen failure, and nonrandomized but treated patients, percentages will be calculated using the number of screened patients as the denominator. All other categories of patients will be presented by treatment group and the percentages will be calculated using the number of randomized patients within each treatment group as the denominator. Reasons for treatment discontinuation will be supplied in tables giving numbers and percentages by treatment group. Patients prematurely discontinued from treatment and/or study, along with reasons for discontinuation, will also be listed.

A summary of the distribution of patients by country and center will also be provided (overall number of patients screened, run-in, randomized, and treated, as well as number of patients randomized, discontinued from study treatment, and discontinued from study for each treatment group).

Patients treated but not randomized, patients randomized but not treated and patients randomized but not treated as randomized will be identified and described in separate listings. The patients of the third category (randomized and not treated as randomized) will be part of efficacy and safety

analyses (see [Section 2.3](#)). Patients randomized but not treated will be included in efficacy analysis. Safety data of patients treated but not randomized will be reported separately.

The randomization strata [HbA1c at Week -1 ($\leq 8.5\%$, $> 8.5\%$), SBP (< 130 , ≥ 130 mmHg) at Week -1 and sulfonylurea use at Week -1 (yes, no)] assigned by IRT will be summarized. The percentages will be calculated using the number of randomized patients as the denominator. The discrepancy between the strata assigned by IRT and the information reported on e-CRF will be listed for all randomized patients.

Kaplan-Meier (KM) plots of the cumulative incidence of double-blind IMP discontinuations due to any reason and due to AEs will be provided for the entire 52-week double-blind treatment period separately (see [Section 2.5.4](#)). A listing of these patients, along with the reason for discontinuation treatment, study completion status and the reason for discontinuation study, will be provided.

For CGM sub-study, the number of patients in each of the following categories will be summarized.

- Screened CGM sub-study population: patients who consented to CGM sub-study
- Patients who did not meet all eligibility criteria for inclusion into the CGM sub-study
- Randomized CGM sub-study population: patients who were randomized and met all eligibility criteria for inclusion into the CGM sub-study as reported in e-CRF.
- Patients who completed CGM sub-study
- Patients who discontinued CGM sub-study and the reason for discontinuation

For patients not meeting all eligibility criteria for inclusion into the CGM sub-study, percentages will be calculated using the number of patients consented to sub-study as the denominator. All other categories of patients will be presented by treatment group and the percentages will be calculated using the number of patients randomized and met all eligibility criteria for inclusion into the CGM sub-study within each treatment group as the denominator. Reasons for CGM sub-study discontinuation will be supplied in tables giving numbers and percentages by treatment group. Patients prematurely discontinued the CGM sub-study, along with reasons for discontinuation, will also be listed.

All important deviations including randomization and drug-dispensing irregularities will be summarized in tables giving numbers and percentages of deviations by randomized treatment group.

Additionally, the analysis populations for safety, efficacy, and pharmacokinetics defined in [Section 2.3](#) will be summarized in a table by number of patients in the randomized population.

- Efficacy population: intent-to-treat (ITT) population
- Efficacy population for sub-study: CGM sub-study population

- Safety population
- PK population

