10.3.3 List of criteria for permanent treatment discontinuation

Patients may withdraw from treatment with the IMP at any time for any reason or this may be the Investigator's decision. Patients should discuss stopping study medication with the site before doing so in order that questions can be addressed, glycemic therapy adjusted, and a follow-up assessment arranged. All efforts should be made to document the reasons for treatment discontinuation and this should be documented in the eCRF.

The following reasons lead to permanent discontinuation:

- At the patient's own request (ie, withdrawal of consent for treatment)
- If, in the Investigator's opinion, continuation with the administration of the study treatment would be detrimental to the patient's well-being

- Intercurrent condition that requires permanent discontinuation of the study treatment as long as the abnormality persists and if the causal relationship of the concerned event and the IMP is possible (according to the Investigator's best medical judgment)
- Pregnancy (in female patients)
- Specific request of the Sponsor.

Any abnormal laboratory value will be immediately rechecked to confirm the result before a decision is made to permanently discontinue IMP for the concerned patient.

For patients who prematurely discontinue the IMP, the assessments planned at the EOT Visit (see [Section 10.1.2.3](#)) will be performed at the Premature EOT Visit scheduled preferably prior to treatment discontinuation or as soon as possible after the time of discontinuation (at the latest at the next scheduled on-site visit). In the case of premature IMP discontinuation, PK samples should not be drawn at the Premature EOT Visit, or at any subsequent visit. The reason(s) for IMP discontinuation will be clearly specified. This EOT assessment may occur at a regularly scheduled or unscheduled visit.

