1 OVERVIEW AND INVESTIGATIONAL PLAN

1.1 STUDY DESIGN AND RANDOMIZATION

This is a Phase 3, multicenter, randomized, double-blind (with single-blind Run-in Phase), placebo-controlled, parallel-group stratified study. Patients are to be randomly assigned 2: 1: 1 to the following 3 treatment groups

- Sotagliflozin 400 mg
- Sotagliflozin 200 mg
- Placebo

All patients will have Screening Period comprised of a Screening Phase of up to 2 weeks and a 4-week Lantus titration/single-blind placebo titration Run-in Phase prior to randomization.

Following randomization, patients will have a 52-week double-blind Treatment Period, and a 2-week post-treatment Follow-up period (patients who prematurely discontinue the study treatment are expected to continue in the study).

At the end of screening period, eligible patients are centrally randomized (using permuted block randomization schedule) via interactive response technology (IRT) in a 2:1:1 ratio to Sotagliflozin 400 mg group, Sotagliflozin 200 mg group and Placebo group. The randomization will be stratified by hemoglobin A1c (HbA1c) ($\leq 8.5\%$, $> 8.5\%$) and systolic blood pressure (SBP) (< 130 mmHg, ≥ 130 mmHg) and sulfonylureas use (Yes, No) at Week -1.

It is anticipated to randomize a total of approximately 560 patients (Sotagliflozin 400 mg: 280; Sotagliflozin 200 mg: 140; Placebo: 140).

Continuous Glucose Monitoring sub-study (CGM sub-study)

Approximately 132 eligible patients participating at a number of pre-selected sites in the United States will also be involved in the CGM sub-study with approximately 66 patients in the sotagliflozin 400 mg arm, 33 patients in the sotagliflozin 200 mg arm and 33 patients in the placebo arm. Two CGM assessment periods are planned: Baseline CGM during Week -1 for 7 consecutive days and post-randomization CGM during Week 18 and 19 for 14 consecutive days. Both patients and investigators will be masked to glucose values.

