- TEAEs (PTs with an incidence ≥5% in any treatment group) by primary SOC, HLGT, HLT, and PT, sorted by internationally agreed order of SOCs. The other levels (HLGT, HLT, PT) will be presented in alphabetic order.

Analysis of all treatment emergent serious adverse event(s)

- All treatment-emergent serious adverse events by primary SOC, HLGT, HLT, and PT, showing the number (%) of patients with at least 1 serious treatment-emergent adverse event, sorted by the internationally agreed SOC order. The other levels (HLGT, HLT, PT) will be presented in alphabetical order.
- All treatment-emergent serious adverse events regardless of relationship and related to IMP, by primary SOC, HLGT, HLT, and PT, showing the number (%) of patients with at least 1 treatment-emergent serious adverse event, sorted by the internationally agreed SOC order. The other levels (HLGT, HLT, PT) will be presented in alphabetical order.

Analysis of all treatment-emergent adverse event(s) leading to treatment discontinuation

- All treatment-emergent adverse events leading to treatment discontinuation, by primary SOC, HLGT, HLT, and PT, showing the number (%) of patients sorted by the internationally agreed SOC order. The other levels (HLGT, HLT, PT) will be presented in alphabetical order

Analysis of adverse events of special interest

Pregnancy and overdose will be included in overall AE summaries if any are reported. ALT increase >3 x ULN is included in laboratory PCSA summary if any.

In addition, the number (%) of patients with an AESI will be summarized by PT and by treatment group. Corresponding listings will be provided as appropriately.

Analysis of events of special interest

Cardiovascular events, bone fracture and DKA

For EOSIs that are adjudicated (ie, deaths, myocardial infarction, stroke, and unstable angina requiring hospitalization, heart failure requiring hospitalization, bone fracture, and diabetic ketoacidosis), the number (%) of patients with an EOSI positively adjudicated by CEC will be summarized by treatment group. All EOSIs sent for adjudication and/or reported by the investigators in the specific AE forms will be listed along with the adjudication outcome.

Renal events

For the EOSI renal events where selected events are adjudicated, the number (%) of patients with any renal events identified in [Table 3](#) in [Section 2.1.4.2](#) will be summarized by treatment group.

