When a patient has more than 1 measurement from the central laboratory for the same laboratory parameter on the same date, the average of the measurements will be used. For the same laboratory parameter, if a patient has more than 1 measurement on different dates for the same

scheduled visit, the value closest to the date of the visit will be used for the scheduled visit. When the values for the same scheduled visit are equidistant, the last value should be used for the scheduled visit. Similar rules will be applicable to a patient who has more than 1 set of measurements for the same vital sign parameter (ie, SBP, DBP, or HR) on the same date.

Time to event analysis

For time to event analysis/KM plot, time to event (eg, treatment discontinuation, rescue therapy, hypoglycemia, etc) is defined as the number of days from the date of the first administration of double-blind IMP (or the date of randomization if not exposed) to the start date of the first occurrence of the event during entire 52-week double-blind treatment period.

Patients who did not experience any event during the entire 52-week double-blind treatment period are considered censored observations. For treatment discontinuation and time to rescue, censoring date is the date of EOT. For time to severe or documented hypoglycemia, censoring date is date of EOT+1 or date of EOS, whichever is the earliest. Date of EOS will be used if date of EOT is not available. Last contact date will be used if date of EOS is not available.

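### The Kaplan-Meier plot of IMP discontinuation due to adverse events censors stops for other reasons, so it overstates the cumulative incidence that it is labelled as showing

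*SAP*

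**What the plan says.** SAP section 2.2 (Disposition of patients) asks for two displays of stopping study drug: "Kaplan-Meier (KM) plots of the cumulative incidence of double-blind IMP discontinuations due to any reason and due to AEs". They cover the full 52 weeks: the plots "will be provided for the entire 52-week double-blind treatment period separately". That section points to SAP section 2.5.4 for the mechanics.

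Under the time-to-event heading of section 2.5.4 the rule is: "Patients who did not experience any event during the entire 52-week double-blind treatment period are considered censored observations". The censoring date follows: "For treatment discontinuation and time to rescue, censoring date is the date of EOT". Time runs from first double-blind dose, or from randomization for patients never exposed. No competing-event rule or estimator appears in either document.

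Protocol section 10.3.3 shows that stops for reasons other than an AE are expected. Its list, introduced by "The following reasons lead to permanent discontinuation", includes the patient's own request, pregnancy and a sponsor request. Protocol section 8.7.1 adds persistent poor compliance. Protocol section 10.3.2 defines permanent discontinuation as a decision never to re-expose the patient to IMP.

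The same information is also to be tabulated. In SAP section 2.2: "Reasons for treatment discontinuation will be supplied in tables giving numbers and percentages by treatment group", with randomized patients as the denominator. In SAP section 2.4.5.2: "All treatment-emergent adverse events leading to treatment discontinuation, by primary SOC, HLGT, HLT, and PT, showing the number (%) of patients".

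**The concern.** The quantity named is a cumulative incidence: the proportion of patients who will have stopped IMP because of an AE by a given time. For the any-reason curve, Kaplan-Meier estimates this, because every stop is an event. For the AE curve it does not.

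A patient who stops by personal choice in Week 10 has no AE-related stop, so the rule censors that patient at EOT. Censoring treats the patient as still able to stop for an AE later, at the same rate as those still on drug. That is impossible once IMP has been permanently stopped. One minus Kaplan-Meier then estimates a hypothetical risk in which nobody stops for any other reason. This is never smaller than the cumulative incidence, and it is larger whenever some AE stops follow other-reason stops.

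At stake is a tolerability figure. A reader taking the Week 52 value from the plot would read a higher percentage than the sponsor's own disposition table gives. If other-reason stops were more common in one arm, part of the visible gap between curves could come from the estimator.

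**Working it through.** **The plan's own figure.** There is none to reproduce. Neither document states an expected discontinuation rate, overall, by arm or by reason. All rates below are assumptions, chosen to show a range.

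**Formula.** Let a be the true 52-week cumulative incidence of AE stops and b that of other-reason stops. With constant cause-specific hazards over the 52 weeks:

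- total cumulative hazard: H = −ln(1 − a − b)
- AE part: h = H × a/(a + b)
- value shown by one minus Kaplan-Meier: 1 − exp(−h)
- value from Aalen-Johansen: a

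**Worked case**, a = 5%, b = 10%: H = −ln(0.85) = 0.1625; h = 0.1625 × 5/15 = 0.0542; 1 − exp(−0.0542) = 5.27%. The excess is 0.27 points.

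| True AE stops | Other stops | Shown by 1 − KM | Excess (points) |
|---|---|---|---|
| 5% | 5% | 5.13% | 0.13 |
| 5% | 10% | 5.27% | 0.27 |
| 5% | 20% | 5.59% | 0.59 |
| 5% | 30% | 5.97% | 0.97 |
| 8% | 15% | 8.69% | 0.69 |
| 8% | 25% | 9.25% | 1.25 |

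Over a from 2% to 10% and b from 2% to 30%, the excess runs from 0.02 to 1.99 points, or about 1% to 20% of the true value.

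**Simulation check.** In 2,000 simulated arms of 280 patients with a = 5% and b = 10%, Kaplan-Meier averaged 5.28% and the crude proportion 5.00%.

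**Dependence on timing.** Without constant hazards, the excess for given a and b depends on order. If all other stops come after the AE stops, there is none. If all come before, the plot shows a/(1 − b): 5%/0.90 = 5.56% for b = 10%, and 5%/0.80 = 6.25% for b = 20%.

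**Between arms**, sotagliflozin versus placebo, assumed rates, constant hazards:

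| True AE stops | Other stops | Shown by 1 − KM | Difference shown (true), points | Ratio shown (true) |
|---|---|---|---|---|
| 5% v 5% | 10% v 10% | 5.27% v 5.27% | 0.00 (0.00) | 1.00 (1.00) |
| 5% v 3% | 10% v 10% | 5.27% v 3.16% | 2.11 (2.00) | 1.67 (1.67) |
| 5% v 5% | 10% v 20% | 5.27% v 5.59% | −0.32 (0.00) | 0.94 (1.00) |
| 5% v 3% | 10% v 20% | 5.27% v 3.35% | 1.92 (2.00) | 1.57 (1.67) |
| 5% v 3% | 20% v 10% | 5.59% v 3.16% | 2.43 (2.00) | 1.77 (1.67) |

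The distortion can be nil, or it can widen or narrow the true difference.

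**The case against.** The strongest reply is that the right number is already planned. Treatment is a fixed 52 weeks, so there is little administrative censoring, and the crude percentage of randomized patients stopping for AEs is essentially the Week 52 cumulative incidence. SAP section 2.2 tabulates that percentage by arm for both the 18-week and 52-week periods and lists the patients concerned. No test is attached to the plot, and SAP section 2.4.5 describes the safety analysis as essentially descriptive. All of this stands, and it is why the point is minor. It also cuts the other way: section 2.5.4 includes never-exposed patients, so plot and disposition table share a denominator and would disagree under the same label. The AE tables in section 2.4.5.2 are a weaker comparator. They use the safety population and treatment-emergent events, so they could differ slightly whichever estimator is plotted.

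The bias is also small beside sampling error. For a 5% proportion the standard error is √(0.05 × 0.95/280) = 1.3 points in the 400 mg arm and √(0.05 × 0.95/140) = 1.8 points in each of the others. Excesses of 0.27 and 0.59 points are under half of either. That is fair, although the bias always runs upward.

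The censoring of other-reason stops is inferred: the SAP never spells it out for the AE curve. It is nevertheless the direct application of the only rule given.

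Finally, a cause-specific Kaplan-Meier curve is a legitimate display if labelled as such. That is correct, and relabelling is therefore an acceptable minimum.

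A reader might infer that the plot will distort the comparison between arms. The documents do not support this as a fact, because they give no discontinuation rates by arm or reason.

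**Conclusion.** The point holds for one curve. As written, the AE-specific plot would carry the label of a cumulative incidence while showing a quantity that is at least as large. Under assumed rates and constant hazards, the excess is about 0.3 to 0.6 points on a true 5% (other stops 10% to 20%) and about 0.7 to 1.3 points on a true 8% (other stops 15% to 25%). Across the wider range examined it is about 0.02 to 2.0 points. An unequal effect between arms is only a possibility, conditional on rates that differ by arm.

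The any-reason curve is correct as planned. No efficacy endpoint, test, power calculation or decision rule depends on the AE plot. This is a low-severity correction to a descriptive figure.

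**What to change.** In SAP section 2.2, plot AE-related IMP discontinuation as the Aalen-Johansen cumulative incidence, with discontinuation for any other reason as a competing event, and keep Kaplan-Meier for any-reason discontinuation. In SAP section 2.5.4, add that for this curve other-reason stops are competing events and are not censored.

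If the sponsor prefers to keep the planned estimator, the minimum is to title the AE plot as a cause-specific Kaplan-Meier curve with other-reason stops censored, and to drop the cumulative-incidence label.

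The cost is a sentence in each of two SAP sections and standard software code. No new data are needed, because reasons for stopping are already recorded in the eCRF under Protocol section 10.3.3.
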